# Description of the clinical study

The present study was planned to examine the effect of a breathing exercise intervention, which was administered to the elderly residents of a nursing home in Ankara, on some physiological parameters, sleep quality and vitality. Breathing exercises can be performed at any time of the day. Due to the effect of some breathing exercises on sleep status, it is not recommended to be applied close to sleeping at night. It is important to evaluate the physical environment in terms of environmental stimuli such as sound, heat, and light, as it affects focusing during breathing exercise. No special clothing or materials are needed during breathing exercises. In order to make the exercise more understandable and fun, various materials have been used in some studies (balloon, wind rose, etc.). In the literature, there are study results showing that physiological effects are seen as a result of applying respiratory exercise to the elderly individuals for three months, three days a week, 30 minutes, in small groups.

Breathing exercises can be done in different ways. Below are the features of the most frequently applied respiratory breathing exercises.

Pursed Lip Exercise: This exercise reduces the number of breaths by keeping the airways open longer. It increases the amount of air flow to the lungs. To apply, it is enough to breathe through the nose and give the lips by contracting. Breathing should be like blowing a candle. The exhalation period should be extended by double the breathing time.

Diaphragmatic Breathing Exercise: The diaphragmatic breathing exercise shows its effectiveness by helping this muscle stretch to work more effectively. While sitting comfortably or lying down, one hand is placed on the chest and the other hand on the abdomen, it is necessary to feel that the abdomen moves out by breathing through the nose. If the abdomen moves more than the chest, the activity is done correctly. Exercise should be repeated as much as possible during the day.

Cough Exercise: Cough exercise is a breathing exercise designed to effectively get rid of mucus without the need to feel very tired. In some individuals, it can create a sense of inhibition when coughing mucus. In a comfortable sitting position, after taking and breathing two normal diaphragm breaths, the third one is breathed and the breath is given twice by making "huh huh sound". This breathing should be like blowing into a mirror to allow the mirror to evaporate. Cough exercise should be less tiring than a traditional cough

### **Research hypotheses**

 $H_01$ : There is no difference in lung functions between the intervention group of elderly individuals subjected to breathing exercises, and those in the control group.

 $H_02$ : There is no difference in cardiac functions between the intervention group of elderly individuals subjected to breathing exercises, and those in the control group.

 $H_03$ : There is no difference in sleep quality between the intervention group of elderly individuals subjected to breathing exercises, and those in the control group.

 $H_04$ : There is no difference in subjective vitality between the intervention group of elderly individuals subjected to breathing exercises, and those in the control group.

## Study design and participants

The study was planned in a pre-test– post-test, randomized controlled (parallel) and experimental design. The study will include individuals aged 65 years and older residing in a nursing home in Ankara, who had a Mini Mental Test score of 2415, had no acute or chronic lung diseases, and had no physical/mental disabilities or limitations and conditions16,17 that might present any obstacle to participate in breathing exercises.

In order for the elderly to perform breathing exercise, he / she should not have acute or chronic lung disease, cognitive functions, physical / mental disability or restriction and disease that would prevent them from participating in respiratory exercise. Especially; ear, brain, spinal cord surgery, acute retinal hemorrhage vertebral fracture and diaphragmatic rupture, hiatus or abdominal hernia, acute myocardial infarction, unstable angina pectoris, severe coronary artery disease, congestive heart failure, severe heart valve disease, acute myocarditis, acute and breathing exercises are not recommended for diseases and health problems such as unstable musculoskeletal injuries, uncontrolled systemic hypertension, severe dementia and behavioral disorders. While examining the inclusion criteria, information about the health status of elderly individuals will be obtained from the files of the nursing home's health unit, and the mini mental test will be applied by the researcher.

After the ethical and institutional permits are obtained for the implementation of the study, the elderly individuals (except the mini metal test score) meeting the researcher nursing home will be identified on 21.01.2019 and the mini mental test measurements of the elderly individuals will be made in the library of the nursing home between 22.01.2019 -28.01.2019. Elderly individuals who agree to participate in the study will be identified by informing the appropriate individuals about the study. In addition, if any of these situations occur during the exercise program, the researcher will be informed by the health unit and the elderly individual will be separated from the study.

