# Application steps in the intervention group

The literature has been examined in determining the duration of respiratory exercise to be applied to elderly individuals in the study group. Taking into consideration the methods and suggestions of all these studies, respiratory exercises are planned in this study. Breathing exercises; Between 18.02.2019 -09.05.2019, for 12 weeks, three days a week (Monday, Tuesday, Thursday) in groups of 5-6 people (2 groups of 6 people, 4 groups of 5 people in total, 10.00-15.30 hours) between each group at the same time of the day, 30 min. will be applied for a while. During the breathing exercise, no special clothing or supplies will be needed. Disruptions in participating in the exercise program will be compensated for at the specified time and day in partnership with the elderly individual and the researcher. The wind rose to be used during the exercise will be provided by the researcher. All types of breathing exercises will be taught to older individuals on the first day of application and will be shown again by the researcher prior to the application throughout the application. Dizziness that may occur during breathing exercise may occur. Elderly individuals will be reminded of this before each application, and if they experience dizziness, they will be asked to wait for the dizziness to pass by pausing the exercise for a short time. The application of the breathing exercise program is as follows;

- I. Pursed Lip Breathing Exercise (using the Wind rose)
- The individual is seated in a position where he feels comfortable and with clothes,
- First, breathe slowly through the nose,
- Lips contract like a whistle
- The wind rose is kept at the level of the mouth at a distance of 25 cm,

• The breath is discharged slowly and for a longer period of time (at least twice the breathing) by blowing from the shrunken lips to the wind rose,

- Power should be used to exhale,
- This process continues until the breath is interrupted,
- A break is taken for 30 seconds, then the procedure is repeated (Total 10 minutes)
- 2 minutes break.
- II. Diaphragmatic breathing exercise
- The active hand is placed on the stomach and the other hand on the chest,
- Breathing slowly through your nose,
- The abdomen is filled with air and the hand rises,
- The rib cage should rise less than the abdomen,
- Then, breathing slowly through the mouth,

- 30 seconds break and the process is completed (10 minutes in total),
- 2 minutes break.

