# Application steps in the control group

No breathing exercise will apply to elderly in the control group. Individuals will continue their daily lives.

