### Post-test

One day after the end of breathing exercise application, between the dates 10.05.2019 - 14.05.2019, elderly individuals will be called by calling from the room telephones in the physical therapy unit. will be re-evaluated in individuals in both groups

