Official Title of the study: Effect of breathing exercise on some physiological parameters, sleep quality and vitality in elderly.

NCT number: not yet have

Date of the document: January 1, 2019

Study population and sample

The population of the study consists of 294 individuals living in the 75th Year Nursing Home Elderly Care and Rehabilitation Center affiliated to Ankara Provincial Directorate of Family and Social Policies. In the sample calculation of the study, taking into account the results of similar studies in the literature with the GPower 3.1.9.4 program, it was calculated that it would be sufficient to take a total of 52 individuals, with a margin of error of 0.05, 80% test power, 26 elderly individuals per group. Considering that such studies may be lost in the process, 20% of the minimum sample number (11 individuals) was added to the study in order not to decrease the statistical power of the research. A total of 32 elderly individuals in the intervention group and 31 elderly individuals in the control group were planned.

Stratified randomization method will be used in the research. Elderly individuals who meet the inclusion criteria will be separated into layers by considering the age (65-74 years -75 years and older) and gender (women-men) after the pre-test data are obtained, and then by simple randomization method using SPSS program in computer environment. will be assigned to the intervention and control groups.

Data collection tools

Research data will be obtained by using the data collection tools mentioned below.

- Introductory Information Form
- Pittsburg Sleep Quality Index (PSQI)
- Subjective Vitality Scale (SVS)
- Physiological Parameters Evaluation Form

Introductory information form

The form was created by the researcher by examining the related literature. In this form, there are 9 closed-ended questions that question the socio-demographic characteristics, health conditions and habits of the elderly.

Pittsburg sleep quality index (PSQI)

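### Read literally, the plan removes people from the study, not only from exercise, when a disqualifying condition arises after randomisation, and no explicit rule keeps them in follow-up or analysis

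*Protocol*

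**What the plan says.** The Study design and participants section lists conditions with which breathing exercise is not advised, ending with "uncontrolled systemic hypertension, severe dementia and behavioral disorders". Its next paragraph sets a rule for the programme period: "if any of these situations occur during the exercise program", then "the researcher will be informed by the health unit and the elderly individual will be separated from the study". It does not say what the situations are; the listed conditions are the natural reading.

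Allocation comes before this rule can act. The SAP assigns people to groups "after the pre-test data are obtained, and then by simple randomization method". The pre-test ends on 3 February 2019, and exercise runs from 18 February to 9 May.

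For 10 to 14 May, the Post-test section says that "elderly individuals will be called by calling from the room telephones in the physical therapy unit" and that the measures "will be re-evaluated in individuals in both groups". It does not mention people removed in between.

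On controls, the protocol says "No breathing exercise will apply to elderly in the control group". On missed sessions, it says "Disruptions in participating in the exercise program will be compensated for at the specified time and day", which concerns attendance and not people who have been removed.

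The SAP adds 11 people to the required 52 to protect power. Its data evaluation section names a dependent-groups t-test and a two-way repeated-measures analysis of variance. It defines no analysis set and no handling of missing post-tests.

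**The concern.** Randomisation makes the two arms comparable as allocated. A rule that drops people afterwards because of a health event can undo that, since the people who remain are selected on something that may be related to the outcome. Lung disease, heart failure and uncontrolled hypertension overlap the SAP's dependent variables (lung function, blood pressure, heart rate, oxygen saturation). Other listed conditions, such as hernia, do not.

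It is also unclear whether the rule reaches controls. The wording is general, but it is tied to the exercise programme, which controls do not receive. If it works mainly in the exercise arm and catches people who are getting worse, the remaining exercisers look better than the full arm would. A two-time-point repeated-measures analysis omits anyone without a post-test, so the planned test would not correct this. Extra recruits restore numbers but do not remove selection.

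**Working it through.** **The plan's own figures.** 20% of 52 is 10.4, rounded up to 11; 52 + 11 = 63 = 32 + 31. The allowance reproduces, and its stated purpose is power only. The documents give no expected number of removals, so the size of any bias can only be illustrated.

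**Assumptions (none from the documents, except the arm sizes of 32 and 31).** Normal outcomes with SD 1, scored so that high is worse; no true effect; pre/post correlation 0.6. A latent trigger has correlation a with the pre-test (0 to 0.6) and b with the post-test (0.5 to 0.8). The k exercisers highest on the trigger are removed and no controls are. The test is a t-test on change, which with two time points equals the group-by-time test.

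**Formula.** Bias in favour of exercise = (b − a) × m, where −m is the mean trigger of those kept.
- k = 1: the highest of 32 standard normal values averages 2.07, so m = 2.07/31 = 0.067.
- k = 3: the highest three average 1.705, so m = 3 × 1.705/29 = 0.176.

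**Results.** False-positive rates are simulated, two-sided, at a nominal 5%.

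| (a, b) | 1 removed | 3 removed |
|---|---|---|
| Mid-range (0.3, 0.6) | 0.3 × 0.067 = 0.02 SD; 5% | 0.3 × 0.176 = 0.05 SD; 6% |
| Most favourable to exercise (0, 0.8) | 0.8 × 0.067 = 0.05 SD; 6% | 0.8 × 0.176 = 0.14 SD; 11% |
| Most adverse to exercise (0.6, 0.5) | −0.1 × 0.067 = −0.01 SD; 5% | −0.1 × 0.176 = −0.02 SD; 5% |

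The sign depends on whether the trigger tracks the post-test more than the pre-test. With a = b the bias is zero.

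**Pre/post correlation 0.8.** The largest admissible pair with a = 0 is (0, 0.6). It gives 0.04 and 0.11 SD, with false-positive rates of 6% and 11%.

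**Losses in both arms.** At (0, 0.8), 3 removed against 2 gives 0.04 SD and 6 against 5 gives 0.03 SD.

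**How different the removed people are.** The SD of the change score is √(2 × (1 − 0.6)) = 0.894. For k = 3 the removed and kept people differ by 1.705 + 0.176 = 1.881 on the trigger. That is 1.881 × 0.3/0.894 = 0.63 change-score SD mid-range and 1.881 × 0.8/0.894 = 1.68 at the extreme. For k = 1 the same steps give 0.72 and 1.91. A sensitivity analysis therefore needs a range. A single shift of 0.5 moves the exercise mean by (3/32) × 0.5 × 0.894 = 0.042 SD, less than even the mid-range bias of 0.053.

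**The case against.** The case for leaving this alone has weight.

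- **Translation.** The English is rough, and the sentence may mean leaving the exercise only. The Post-test section re-evaluates both groups with no stated exclusion. A reader might infer that the plan forbids follow-up of removed people; it does not say so. What stands is that no explicit rule keeps them in.
- **Similar detection in both arms.** The health unit reports the condition, not the exercise leader, and that unit's files are used to screen everyone at entry. This supports similar reporting in both arms, where the illustrated bias is small. The wording about the exercise programme leaves it unsettled.
- **Few removals.** Entry screening excludes these conditions and the programme lasts 12 weeks. A reader might take a larger case as the size of the problem: 6 removed from the exercise arm alone, at the extreme pair, gives 0.8 × 0.320 = 0.26 SD and a false-positive rate of about 22%. The documents do not support that. They give no removal rate and do not establish one-arm removal, and 6 condition-driven removals in one arm are unlikely after screening.

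A reader might also infer that the trial is biased towards exercise. The text shows only that it can be; under some assumptions the sign reverses slightly. Sending the analyst coded groups does not answer the point, because coding does not decide who is analysed.

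**Conclusion.** The point holds as a gap in the text. As written, the plan permits outcome-related exclusion after randomisation, and neither document clearly keeps removed people in the post-test or the analysis. The likely effect is small: about 0.02 to 0.05 SD mid-range for 1 to 3 one-arm removals, no more than 0.14 SD at the extreme, and no more than about 0.04 SD if the arms lose similar numbers. Every correlation and removal count behind these figures is assumed, as is removal of exactly the people highest on the trigger. The case for change rests on the missing follow-up and analysis rules, not on the simulated bias. It is a cheap improvement, and it must be made before the May post-test window, after which the measurements cannot be recovered.

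**What to change.** Leave the decision to stop exercise unchanged.

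**Protocol, Study design and participants.** State which situations the rule refers to. Replace the words that end study participation with a statement that the person stays in the assigned group and is invited to the 10 to 14 May post-test for the questionnaires and any measurement judged safe, unless consent is withdrawn. State that health-unit reporting is the same in both arms.

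**SAP, evaluation of the data.**
- Everyone with a post-test is analysed in the arm randomised, whatever the attendance.
- People without a post-test are absent from the two-time-point analysis of variance and are reported by arm and reason.
- A sensitivity analysis assumes that they changed worse than the observed people in their arm by, for example, 0.5, 1.0, 1.5 and 2.0 SD of the change score. It does so first in the exercise arm only, then in both arms, and reports where the conclusion changes.

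**Cost.** A few sentences in each document, and a few extra post-tests for residents of the same home. The estimate may be slightly diluted by people who stopped exercising. Some values will still be missing where measurement is unsafe; the sensitivity analysis shows how much they could matter but does not recover them.

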### Clinical trial facility location and property

The research was carried out in the 75th Year Nursing Home Elderly Care and Rehabilitation Center, affiliated to Ankara Family and Social Policies Provincial Directorate. The institution, which has a capacity of 294 people, has a director and three deputy directors, 10 nurses, three social workers, two psychologists and a sociologist and four physiotherapists. Breathing exercises program is not included in the routine practices of the nursing home. In addition,

activities such as hobby works, handicrafts, music studies, sports activities, exhibitions and kermes activities, excursions, cinema days, panel - conferences are carried out. Exercise will be held in the group activity hall of the physical therapy unit, which is determined as the most suitable area for elderly individuals and exercise application with the joint decision of the nursing home management and researcher.

## **Prevention of interaction of groups**

In order to reduce the interaction of elderly individuals in the intervention and control groups with respect to breathing exercise, the exercise room of the physical therapy unit located in a different area than the section where the elderly live is determined as the application area of the exercise. In addition, even if there is a sharing about breathing exercise among elderly, the application should be applied regularly and consciously under the supervision of a specialist in order to reveal the desired success. In this sense, it is thought that the interaction between the groups has no significant effect.

# **Pre-test**

The pre-test application is planned to be done between 29.01.2019 -03.02.2019. In the physical therapy unit of the nursing home, a suitable area will be determined by the researcher and specialist physiotherapist, and measurement devices will be placed, elderly individuals in both groups will be called from the room phone and called for measurement. In order to prevent the data from being affected by the measurements, introductory information data sheet, Pittsburg Sleep Quality Index, Subjective Vitality Scale will be applied, individuals will be rested during this period, and then cardiological parameters will be evaluated, and finally lung functions will be evaluated.

A manual sphygmomanometer and a pulse oximeter device will be used to assess heart function. Sphygmomanometer is of Perfect Aneroid type. The manometer chamber and the spoon spoon are nickel plated chrome. The manometer is 48 mm in diameter, the cuff outer cloth dimensions are 13x47 cm (+/- 2 cm), the cuff outer cloth is hooked, the cuff inner tube hoses are made of double-layer, vulcanized rubber. It is suitable for adult use. Finger pulse oximetry device has arterial oxygen saturation and pulse measurement feature. It provides a graphical view of the pulse. It is suitable for all ages. Evaluation steps are as follows;

• The individual is informed before evaluating his heart functions.

• The individual is placed in a position where the individual can be comfortable from the measurement. He should not have used tea, coffee and cigarettes until 15 minutes before the measurement.

- The individual is rested for 3-5 minutes
- Heart rate is measured from the radial artery for one minute

• For the systolic / diastolic blood pressure, the appropriate arm is selected, the clothes are relaxed / removed, the arm is positioned (must be at 45 heart level), the appropriate sleeve is selected (wrap the arm sufficiently). Next, the location of the brachial artery is determined, the air of the cuff is completely evacuated, the lower edge of the cuff is taken 2-2.5 cm above the place where the brachial artery is palpated, the middle point of the cuff is placed on the brachial artery. The receiver of the stethoscope is placed on the brachial artery without touching the sleeve and clothes and the earpiece is placed on the ear, the cuff is inflated to 30 mmHg above the previously determined systolic blood pressure value, then the cuff air is discharged to be 2-3 mmHg / second.

• Blue, black, green, brown, red nail polish, if any, in the individual before the oxygen saturation measurement is deleted, artificial nail is removed,

- It is placed on the hand and / or toenail of the light source part of the pulse oximeter,
- Measurements are made for 30 seconds and then the device is removed from the finger
- The data are recorded on the data form created by the researcher.

Evaluation of lung functions will be done in the presence of a specialist physiotherapist. The specialist physiotherapist does not know the elderly individuals in the experimental and control groups. Spirometry will be used to evaluate lung function. Spirometry is the basic device of respiratory function test laboratories. It consists of the electronic part where the measurement is made and the mouthpiece that the patient breathe. Cosmed Pony FX - Desktop Spirometer and disposable mouthpieces suitable for the device will be used in the study. This type of spirometer enables testing without the need for a computer. It has an internal memory where patient information can be stored. It is used with two-way digital turbine flowmeter. Pulse function test measurement application steps are as follows;

- Elderly individuals are informed before spirometry is applied.
- The height of the elderly person, body weight is measured and recorded with his age
- Individual disposable mouthpiece is placed in the entry section of the tool.

• The individual puts the mouthpiece in his mouth with his lips, but not to bite with his teeth. It is important that the lips close well. Otherwise, leakage will occur. This causes incorrect measurement.

• The nose of the individual who is connected to the spirometer device with the help of a mouthpiece is closed with a special latch before the measurement.

- The individual breathes calmly first (4-5 times)
- It takes a hard, deep and fast breath after normal breathing.

• It is also fast, challenging and exhaled with the command to exhale. Breathing should take at least 6 seconds.

• This process must be repeated at least 3 times.

The test results are compared with the expected values (predicted values) pre-calculated in healthy individuals of the same age, height and gender by the software found in the spirometer

device and expressed as a percentage of these values. The obtained results will be sent to the researcher within 15 days in pdf format by the authorized firm of the spirometer device.

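### Blood pressure and oxygen saturation are measured without a repeat reading, a same-arm rule or one fixed oximeter site, which adds avoidable random error to their pre-post change

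*Protocol*

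**What the plan says.** The Pre-test section of the Protocol lists the cardiac steps in order, and the Post-test section says only that both groups will be assessed again.

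- **Blood pressure, arm.** The choice is left open: "For the systolic / diastolic blood pressure, the appropriate arm is selected". No side is recorded and nothing ties the post-test to the pre-test arm.
- **Blood pressure, inflation.** "the cuff is inflated to 30 mmHg above the previously determined systolic blood pressure value". The only palpation described serves to position the cuff: "the lower edge of the cuff is taken 2-2.5 cm above the place where the brachial artery is palpated".
- **Blood pressure, replication.** The steps stop at deflation. No second reading, interval or average is mentioned.
- **Oxygen saturation.** The device is introduced thus: "Finger pulse oximetry device has arterial oxygen saturation and pulse measurement feature". The placement step reads: "It is placed on the hand and / or toenail of the light source part of the pulse oximeter". The next step has the device taken off the finger.
- **Heart rate.** "Heart rate is measured from the radial artery for one minute".
- **Spirometry, same visit.** Replication is explicit: "This process must be repeated at least 3 times".

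The SAP (Dependent variables) lists systolic and diastolic pressure, heart rate and oxygen saturation as outcomes. Under Evaluation of the data it analyses pre-to-post change with paired t-tests and a two-way repeated-measures analysis of variance.

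**The concern.** The cardiac steps are detailed enough to give the cuff-edge distance, the deflation rate and the colours of nail polish to remove. At that level of detail, the missing replication and site rules are likely to be carried out as written: one blood pressure reading, on whichever arm seems suitable that day, and an oximeter on a finger or a toe. The authors did ask for repeats where they wanted them, in spirometry.

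H02 is tested on change from pre-test to post-test, so reading error enters twice, once per visit. If the arm or the oximeter site differs between visits, the within-person difference between sites enters as well. None of this variation has to do with the exercise. With 26 per group as the calculated minimum, avoidable variance directly costs the chance of detecting an effect.

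**Working it through.** **1. The plan's own figures.** The SAP gives 26 per group, 52 in total, at 0.05 and 80% power, and adds 20%. 52 × 1.20 = 62.4, rounded up to 63 = 32 + 31, which matches the planned allocation. The 26 per group cannot be reproduced because no effect size, SD or design outcome is stated. Solving backwards with the noncentral t for two independent groups, it corresponds to d = 0.79 two-sided or d = 0.70 one-sided. No figure in the documents is contradicted.

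**2. Model for the change in systolic pressure.** All inputs are assumptions, because the documents give none:

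- t, true between-person SD of change: 8-12 mmHg
- e, SD of one reading within a visit: 5-7 mmHg
- a, SD of the inter-arm difference: 0-5 mmHg
- half of participants change arm between visits

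One reading per visit, arm not fixed: Var = t² + 2e² + 0.5a².

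Mean of two readings per visit, same arm: Var = t² + 2(e²/2) = t² + e².

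**3. Results.**

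| t, e, a | One reading, arm free | Two readings, same arm | Reduction |
|---|---|---|---|
| 12, 5, 0 (smallest) | 144 + 50 + 0 = 194 | 144 + 25 = 169 | 25/194 = 12.9% |
| 10, 7, 5 | 100 + 98 + 12.5 = 210.5 | 100 + 49 = 149 | 61.5/210.5 = 29.2% |
| 8, 7, 5 (largest) | 64 + 98 + 12.5 = 174.5 | 64 + 49 = 113 | 61.5/174.5 = 35.2% |

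In the middle row the SD falls from √210.5 = 14.5 to √149 = 12.2 mmHg.

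**4. Which change does the work.** The arm rule alone removes 0.5a². In the middle row that is 12.5/210.5 = 5.9%, against 49/210.5 = 23.3% for the second reading. Over the whole grid the arm share peaks at t = 8, e = 5, a = 5: 12.5/(64 + 50 + 12.5) = 12.5/126.5 = 9.9%. The arm share is zero if the inter-arm SD is zero.

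**5. Translation into power (illustration).** Suppose 26 per group gives 80% power for systolic change measured as written, so d = 0.79 two-sided. Dividing d by √(1 − reduction) gives 0.79/√0.871 = 0.85 to 0.79/√0.648 = 0.98, and power of 85% to 94%. Suppose instead that the 80% presumed the cleaner measurement. Then d shrinks to 0.74 to 0.64, and power is 74% to 62%. The documents do not say that the calculation concerns blood pressure at all.

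A simpler check ignores the arm and treats the outcome as one measurement with assumed single-reading reliability 0.6 to 0.95. Averaging two readings then moves 80% power to 87.9% at reliability 0.6 and to 81.0% at 0.95. The gain can therefore be anything from trivial to material.

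**6. Oxygen saturation.** No arithmetic is possible. The device description and the removal step both say finger, while the placement step also allows a toe. The steps cannot all hold for one measurement site.

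**The case against.** The strongest reply is that much of this reads procedure into silence, and several stronger readings do fail.

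- **One reading, arm chosen anew.** A reader might take these as stated rules. They are what the text permits. No count is given, the SpO2 step speaks of measurements in the plural, and a criterion of suitability could well lead to the same arm twice.
- **No systolic value at the pre-test.** A reader might infer that the inflation step is impossible. The documents do not show that. Health-unit files are consulted at screening and may hold a value, or an estimate by palpation may simply be undescribed. The defect is an unstated source.
- **Anchoring on the pre-test value.** This would need the pre-test reading to be the post-test reference, which no section says. An inflation target is also not the reading itself.
- **All H02 outcomes affected.** Heart rate has a named site and a full-minute count. Arm and inflation concern blood pressure, and the finger or toe concerns SpO2.
- **A site shift in SpO2 that mimics an effect.** The documents give no size for such a shift. If it falls at random across groups, it adds noise to the comparison, not a difference.

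It is also fair to say that the translation is awkward, so the toe may be a slip of wording, and that a second reading is a design choice that the documents do not contradict.

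What stands is that someone following the steps would be free to take one reading, change arms and use a toe, and that a better procedure is available with the same staff and devices.

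**Conclusion.** The point holds for blood pressure and SpO2 as a loss of precision. The procedure is the same for both groups, and the SAP randomises after the pre-test, so pre-test error cannot depend on allocation. Random error of this kind widens the interval and lowers power, and leaves the raw group difference unbiased. That rests on post-test arm and site choices being unrelated to group. The Protocol states that the physiotherapist present at the lung function tests does not know the groups, but says nothing of the kind about whoever takes the cardiac readings. This is no evidence of bias, but it is a further reason to fix the procedure in writing.

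The size is a reduction of about 13-35% in the variance of systolic change, mostly from the second reading. It rests wholly on the assumed SDs and the assumed half of participants switching arm. The direction holds whenever reading error is not zero; the size cannot be settled from the documents. No size can be given for diastolic pressure or SpO2. This is a cheap improvement, not an error that invalidates the H02 analysis.

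**What to change.** In the cardiac steps of the Pre-test section, and by reference in the Post-test section:

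1. Take two blood pressure readings at each visit and analyse their mean. State this in the SAP as the analysed value.
2. Record the arm at the pre-test and use the same arm at the post-test.
3. Remove the toe option from the oximeter step and use the same finger at both visits.
4. State that the reference systolic value for inflation is obtained at that same visit.

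The cost is about 2-3 extra minutes per participant per visit, two or three fields on the physiological parameters form, and a few lines of text. No new equipment or staff are needed, and the sample size is unchanged.
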